# Activity monitoring:

We will use ActivPAL activity monitoring system over a 5 day period to record patients activity. Software algorithms are used to classify an individual's free-living activity into periods spent sitting, standing and walking. This information can be used to estimate daily energy expenditure and changes in the activity profile. Patients will undergo this assessment pre-operatively and at 1 and 2 years post-operatively.

# CT scan protocol:

Imaging of three regions is required; hip, knee and ankle as detailed below.

	Hip	Knee	Ankle
kV	100	100	100
mAs	80	100	45
Scan length	~ 50 mm	~200mm	~ 50 mm
Collimation	4 mm	1 mm	4 mm
FOV	Includes femoral head	Must include 100mm above and below the joint- line between the femur and the tibia	Must include the talus and distal tibia

# CT analysis:

Pre-operative CT scans will be used to plan robotic surgery and measure pre-operative joint alignment. Post-operative CT scans will be used to:

- 1. Validate the intra operative implant alignment values recorded by the Robotic System.
- 2. Describe the differences in absolute implant positioning in order to characterise the differences between the two surgical philosophies being employed.

- 3. Compare the degree of variation from the planned position of implants and the actual position of implants between the two groups.
- 4. Determine if the femoral and tibial components are correctly aligned with respect to each other, checking for example for possible mismatch of rotation between the components. 2D and 3D models of the replaced knee will be generated form CT data, these will be used to determine the following variables for each patient:

**Mechanical Axis Alignment of the knee joint** - Measured through the centre of the hip (centre of the spherical femoral head), centre of the knee (centre of the tibial plateau) and centre of the ankle (centre of the talus).

*Varus / Valgus Alignment (Alignment in coronal plane) -* Femoral Coronal Angle measured as the angle between: The femoral mechanical axis (centre of the hip and the centre of the knee) and the medial/lateral axis of the condylar implant.

Tibial Coronal Angle measured as the angle between: The tibial mechanical axis (centre of the knee and the centre of the ankle) and the medial/lateral axis of the tibial implant.

**Slope Alignment (Alignment in sagittal plane) -** Tibial Slope measured as the angle between: Tibial implant / bone interface and the tibial mechanical axis.

Femoral Flexion measured as the angle between: Femoral mechanical axis and Femoral implant peg axis.

**Rotation Alignment (axial plane)** -Femoral Rotation measured as the posterior condylar angle, angle between: the surgical transepicondylar axis (TEA), connected the centre of the sulcus of the medial epicondyle and the most prominent point of the lateral epicondyle and the posterior condylar axis of the implant.

Tibial rotation measured as the angle between: the perpendicular line to the tangent of the posterior rim of the tibial plateaus and the tangent to the AP axis of the tibial implant.

# 11.1. Assessment of efficacy/effectiveness

This is an explanatory randomised controlled trial and as such as concerned with demonstrating efficacy rather than generalisable effectiveness.

Efficacy will be determined in a number ways. Kinematic measures as outlined above will determine if the novel Robotic Assisted Bi-UKA surgery can produce measurable improvements in knee kinematics and kinetics which result in more normal gait pattern than is typically achieved with traditional TKA surgery. This will be determined at 1 year post-operatively using full gait analysis and functional electrogoniometry. Improved gait is likely to be associated with improved clinical outcome scores, reduced pain, higher activity levels, lower physical impairment and greater implant longevity.

# Improved function and activity will be measured using:

- Stair Climb Test
- Timed Up and Go Test UCLA Activity Score

# Improved clinical outcome will be measured using:

- Mechanical alignment of the knee
- Oxford Knee Score, New American Knee Society Score, Forgotten Joint Score
- Analgesic use, Pain Score
- Satisfaction

# Decreased patient impairment will be measured using:

- Knee joint proprioception
- Active and passive Range of Motion
- Isometric Quadriceps strength
- Progression of OA in the contralateral knee will be measured using Kellgren and Lawrence grading of knee X-rays

### Surgical accuracy will be measured using:

• CT analysis of accuracy of implant positioning in the sagittal, coronal, axial planes.

We have used the CT and gait analysis methodology described here in several recent studies and therefore the methodology for each has been established and validated. We have a number of manuscripts that have been or are due to be published that report data from UKA or TKA cohorts using these methodologies.

#### 11.2. Assessment of safety

Patient safety will be assessed by comparing complications of surgery / adverse events related to surgery (infection, DVT, PE, delayed discharge from hospital, manipulation under anaesthetic, re-operation and implant survivorship). Safety of the RIO Robotic device will be assessed by recording system errors and malfunctions, as well as by assessing accuracy of implantation.

#### 12. Safety

## 12.1. Definitions

### 12.1.1. Adverse Events (AE) An

#### AE or adverse event is:

Any untoward medical occurrence in a patient or other clinical investigation participant taking part in a trial of a medical device, which does not necessarily have to have a causal relationship with the device under investigation.

An AE can therefore be any unfavourable and unintended sign (including an abnormal laboratory finding), symptom or disease temporally associated with the use of the device, whether or not considered related to the device.

## 12.1.2. Adverse Device Effect (ADE)

All untoward and unintended responses to a the medical device.

The phrase "responses to a medical device" means that a causal relationship between the device under investigation and an AE is at least a reasonable possibility, i.e., the relationship cannot be ruled out.

All cases judged by either the reporting medically qualified professional or the sponsor as having a reasonable suspected causal relationship to the device qualifies as a device effect.

This also includes any event resulting from insufficiencies or inadequacies in the instruction for use or deployment of the device and includes any event that is a result of a user error.

#### 12.1.3. Serious Adverse Event (SAE)

SAE is an adverse event that

- Led to death
- Led to fetal distress, fetal death or congenital abnormality or birth defect.
- Led to serious deterioration in the health of the subject that
  - Resulted in a life-threatening illness or injury
     NOTE: The term "life-threatening" in the definition of "serious" refers to an event in which the participant was at risk of death at the time of the

event; it does not refer to an event which hypothetically might have caused death if it were more severe.

- Resulted in a permanent impairment of a body structure or a body function
- Required in-patient hospitalisation or prolongation of existing hospitalisation
- Resulted in medical or surgical intervention to prevent permanent impairment to a body structure or a body function
- Other important medical events\*

\*Other events that may not result in death, are not life threatening, or do not require hospitalisation, may be considered a serious adverse event when, based upon appropriate medical judgement, the event may jeopardise the patient and may require medical or surgical intervention to prevent one of the outcomes listed above

To ensure no confusion or misunderstanding of the difference between the terms "serious" and "severe", which are not synonymous, the following note of clarification is provided:

The term "severe" is often used to describe the intensity (severity) of a specific event (as in mild, moderate, or severe myocardial infarction); the event itself, however, may be of relatively minor medical significance (such as severe headache). This is not the same as "serious," which is based on patient/event outcome or action criteria usually associated with events that pose a threat to a participant's life or functioning.

Seriousness (not severity) serves as a guide for defining regulatory reporting obligations.

# 12.1.4. Serious Adverse Device Effect (SADE)

A serious adverse device effect (SADE) is any untoward medical occurrence seen in a patient that can be attributed wholly or partly to the device which resulted in any of the characteristics a characteristics of a serious adverse event.

A SADE is also any event that may have led to these consequences if suitable action had not been taken or intervention had not been made or if circumstances had been less opportune.

All cases judged by either the reporting medically qualified professional or the sponsor.

#### 12.1.5. Unanticipated Serious Adverse Device Effect (USADE)

Any serious adverse device effect on health or safety or any life-threatening problem or death caused by, or associated with a device, if that effect, problem, or death was not previously identified in nature, severity or degree of incidence in the investigational plan or application (including a supplementary plan or application), or any other unanticipated serious problem associated with a device that related to the rights, safety or welfare of the subject.

#### **12.1.6 Device deficiency**

Inadequacy of a medical device related to its identity, quality, durability, reliability, safety or performance, such as malfunction, misuse or use error and inadequate labelling.

### **12.2. Reporting and Documentation**

# 12.2.1. Reporting and Documentation of Adverse Events and Adverse Device Effects

Adverse Events and Adverse Device Effects will be documented on Adverse Event Report Forms for the duration of the investigation. Furthermore the outcome of such complications will be documented and any changes in outcome updated during the course of the study. Each adverse event and adverse device effect must be assessed for seriousness, causality and expectedness. All AEs will be reported to the Chief Investigator.

### 12.2.2. Reporting of SAEs, SADEs, UADEs to the sponsor

The following events should be reported to the sponsor

- any SAE,
- any Investigational Medical Device Deficiency that might have led to a SAE if
   a)suitable action had not been taken or
  - b) intervention had not been made or
  - c) if circumstances had been less fortunate
- new findings/updates in relation to already reported events

All SAE/SADE/USADEs must be reported to the PV office within 24 hours of the investigator becoming aware of the event; regardless of relationship to the device. The PV office should remain blinded to the participants allocation and therefore causality unless there is a clinical need to unblind for patient safety. The chief investigator should assess all the causality and expectedness of all SAEs occurring within the study using the information below and their clinical judgement

SAEs are reported using the Serious Adverse Event Report Form for a Non-CE-marked Medical Device. Device deficiencies should be reported using the Device Deficiency Report

#### Definitions of related and unanticipated events:

• "Related" – that is, it resulted from administration of any of the research procedures, and

• "Unanticipated"- that is, the type of event is not listed in the protocol as an expected occurrence.

Anticipated adverse events that can occur with any orthopaedic surgery include: Re-admission, implant failure, implant removal or revision, periprosthetic fracture, infection (superficial or deep), wound washout for infection, deep vein thrombosis, pulmonary embolism, stroke, neurovascular complications, post-operative confusion, pain, decreased range of motion and swelling of the leg. Anticipated adverse events that may occur due to the use of the trial device or trial specific procedures include: Damage to lateral ligaments, damage to the patellar tendon, damage to the anterior cruciate ligament, and early loosening of the device components (within 2 years of surgery). Events will be followed up until resolution, any appropriate further information will be sent by the research team in a timely manner.

The Sponsor acting on behalf of the manufacturer has a legal obligation to report all events that need to be reported to the MHRA immediately (without any unjustifiable delay) after a link is established between the event and the device, within the following time periods:

• SAEs that indicate the death of a participant, an imminent risk of death, serious injury, or serious illness that requires prompt remedial action for other participants, users or other persons, or a new finding relating to a previously reported SAE of this seriousness must be reported to the MHRA no more than 2 calendar days following awareness of the event by the sponsor

• Other reportable events not described above or follow up information relating to those events must be reported to the MHRA within 7 days of the sponsor becoming aware of the event

• USADES will be submitted to the REC within 15 days of the PV office becoming aware of the event.

# 12.2.3. Reporting of SAEs, SADEs, UADEs to the manufacturer

### Device deficiencies

The PV office will report any device deficiencies to the manufacturer following unblinding of the participants allocation.

Device deficiencies due to the MAKO Restoris MCK will be reported to the manufacturer; MAKO Surgical Corp following unblinding.

Device defidiencies due to the comparator Zimmer NexGen LPS TKA will be reported to the Incident Reporting and Investigation Centre (IRIC – part of NHS National Services Scotland) via the following means. http://www.hfs.scot.nhs.uk/online-services/incident-reporting-and-investigation-centre-iric/how-to-report-an-adverse-incident/

Unblinded members of staff should ensure that they do not allow blinded members of the trial team, the sponsor, data managers and trial statisticians to access unblinded SAEs

#### 12.3. Annual Report

In addition to the above reporting the Chief Investigator will submit once a year, for the duration of the trial, or on request a progress/safety report to the REC and NHS GG&C R&D.

#### 13. Discontinuation or withdrawal of participants from the study

Each participant has the right to withdraw study at any time. In addition, the investigator may discontinue a participant from the study at any time if the investigator considers it necessary for any reason including:

- Ineligibility (either arising during the study or retrospective having been overlooked at screening)
- Significant protocol deviation

- Significant non-compliance with treatment regimen or study requirements
- Consent withdrawn
- Lost to follow up

The reason for withdrawal will be recorded in the CRF.

# Withdrawal of patients at the time of surgery:

Any patient found to have grade 4 (Kellgren and Lawrence) changes on the lateral facet at the time of surgery, that was not evident pre-operatively) will be withdrawn from the Trial and will be given a Total Knee Arthroplasty outwith the Trial. The patient will be withdrawn even if they have been randomised to receive a Total Knee Arthroplasty within the study. The justification for the latter scenario is to ensure that both Trial groups remain balanced in terms if patient pathology and extent of disease.

Bi-UCKA surgery aims to treat patients with disease in both the medial and lateral compartments of the knee. Any patient who is found to have only minimal disease in one of the compartments at the time of surgery which was thought to be more severe pre-operatively, will remain within the study. The rationale for this is that the standard of care treatment for unilateral osteoarthritis of the knee in the majority of centres in the UK is a Total Knee Arthroplasty and therefore as Bi-UCKA is an alternative to a Total Knee Arthroplasty it is acceptable to use this in these cases.

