# 7. Research design

The study will be a prospective randomised double blinded controlled study comparing two surgical techniques. Patients randomised to Group 1 of the study (controls) will receive a standard TKA. Patients randomised to group 2 will receive Bi-UKA surgery carried out with the aid of Robotic Assistive Technology.

The study will be blinded, meaning that researchers undertaking post-operative patient assessments will not be informed which intervention patients have been randomised to receive. Surgeons involved in the study will be aware of which arm of the study patients have been randomised to. However, all post-operative data relating to the study will be collected by independent research nurses and no post-operative data will be collected by the operating surgeons. Patients will not be directly informed which arm of the study they have been randomised to.

Randomisation will be carried out after informed consent has been obtained and prior to the day of surgery. This duty will be carried out by research nurses and not by the investigators. A webbased interface will be used to access a dedicated randomisation programme created by the NIHR registered Clinical Trials Unit at the University of Aberdeen's Centre for Healthcare Randomised Trials (CHaRT) which is supporting the trial. Randomisation for the study will be stratified by surgeon.

Pre-operative and post-operative data collection will be carried out by research nurses at the time points specified in this protocol. Data will be collected on paper Case Report Forms (CRF) and this will be transcribed into a secure database. We have successfully used similar methodology for several other randomised controlled trials.

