# 16. Statistical analysis

All statistical analyses will be governed by a comprehensive Statistical Analysis Plan, which will be agreed by the research group and approved by the independent Data Monitoring Committee. The primary outcome (at 1 year) will be analysed according to the intention to treat principle, and will use a mixed effects logistic regression model, with surgeon fitted as a random effect. We will also consider a per protocol analysis, including those who received the surgery as intended. We would adjust this primary analysis for baseline gait i.e. the primary outcome measured at baseline. At present there are no subgroup analyses proposed for the primary outcome.

Analysis of secondary outcomes will be similar to that for the primary outcome, except using generalised linear models appropriate to the distribution of the specific outcome (e.g. linear or logistic). At present there are no count data (e.g. Poisson or negative binomial regression) or time to event outcomes (e.g. Cox proportional hazards regression) being considered. For the secondary outcomes that have serial measures post randomisation (e.g. 3m, 1 y, 2y, 5y, 10y) we will use repeated measures models to explore any possible time development of a treatment effect we identify.

As indicated above, we will explore the robustness of any findings we report to patterns of missing data, most prominently using multiple imputation models exploring missing data mechanisms assumed to be generated under a 'missing at random' assumption. There will be no formal adjustment for multiple comparisons given the explanatory rather than confirmatory nature of this study.

The independent Data Monitoring Committee will not conduct any formal interim analyses of the efficacy outcomes – their role will be primarily concerning safety.

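### The in-theatre withdrawal rule takes randomised patients out of the trial on an unblinded surgeon's finding and makes no provision for follow-up, so the declared intention-to-treat primary analysis cannot be delivered as written

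*Protocol*

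**What the plan says.** Protocol Section 7 fixes the order of events: "Randomisation will be carried out after informed consent has been obtained and prior to the day of surgery". It also says who is unblinded: "Surgeons involved in the study will be aware of which arm of the study patients have been randomised to".

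Protocol Section 13, under the heading on withdrawal at the time of surgery, then says that a patient with Kellgren and Lawrence grade 4 change on the lateral facet, not evident before the operation, "will be withdrawn from the Trial and will be given a Total Knee Arthroplasty outwith the Trial". The rule covers the control arm as well: "The patient will be withdrawn even if they have been randomised to receive a Total Knee Arthroplasty within the study". The reason given is "to ensure that both Trial groups remain balanced in terms if patient pathology and extent of disease".

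The general part of Section 13 also lets the investigator discontinue a participant. The listed reasons include significant protocol deviation and "Ineligibility (either arising during the study or retrospective having been overlooked at screening". It does not say whether such patients continue to attend visits or whether their data are kept.

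Protocol Section 16 states: "The primary outcome (at 1 year) will be analysed according to the intention to treat principle". A per-protocol analysis is mentioned separately, as something to be considered.

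**The concern.** An intention-to-treat analysis needs the 1-year gait outcome for everyone randomised, in the arm to which they were allocated. A patient who leaves the trial in theatre and is treated outside it has no planned 1-year gait assessment. A statistical analysis plan can define which patients belong to which analysis set, but it cannot recover measurements that were never taken.

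Who makes the decision also matters. The finding is judged during the operation by a surgeon who knows the arm, and no blinded or independent confirmation is described. In the Bi-UCKA arm the finding changes the operation. In the TKA arm the patient receives a TKA either way, so there is less reason to look for the finding or record it. The scale is the one that Section 11.1 applies to radiographs ("Kellgren and Lawrence grading of knee X-rays"), and no criterion is given for its use in theatre. If detection differed between arms, the patients remaining would no longer be a randomised comparison.

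**Working it through.** **1. The sections side by side**

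- Section 7: allocation comes before the day of surgery, so any withdrawal in theatre is post-randomisation, and the surgeon is unblinded.
- Section 13, time of surgery: withdrawal from the trial is mandatory on the finding. Continued follow-up is not mentioned.
- Section 13, revision: patients who are revised are expressly kept on scheduled visits. The document therefore states continued follow-up where it intends it.
- Section 16: the primary analysis is intention to treat.

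The second and fourth items cannot both be carried out.

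**2. The plan's own sample size reproduces**

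Inputs from Section 15: 23% against 60%, 90% power, 5% level (two-sided), no continuity correction, 10% loss.

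- With p̄ = (0.23 + 0.60)/2 = 0.415, n = [1.960√(2p̄(1−p̄)) + 1.282√(0.23×0.77 + 0.60×0.40)]² / 0.37² = 35.1, rounded up to 36 per group. Power at 36 is 0.907.
- 36/0.90 = 40 per group. The allowance covers loss to follow-up and nothing else.

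No figure in Section 15 is disputed.

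**3. What unequal detection would do**

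The documents give neither the prevalence of the finding nor the outcome in such patients. The following are assumptions: no true treatment effect, a biphasic rate of 40% without and 10% with the finding, 36 per arm before withdrawal, and every case withdrawn in the Bi-UCKA arm. With prevalence q and a fraction d of cases detected in the TKA arm:

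- Bi-UCKA rate after withdrawal = 0.40
- TKA rate after withdrawal = [(1−q)×0.40 + q(1−d)×0.10] / [(1−q) + q(1−d)]

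| q | d = 1 (equal) | d = 0.5 | d = 0 | Type I error at d = 0 |
|---|---|---|---|---|
| 5% | 0 points | 0.8 | 1.5 | 0.052 |
| 10% | 0 points | 1.6 | 3.0 | 0.058 |
| 20% | 0 points | 3.3 | 6.0 | 0.079 |

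Example at q = 10%, d = 0: TKA rate = 0.90×0.40 + 0.10×0.10 = 0.37, a difference of 3.0 points. With equal detection there is no bias and the type I error is 0.050.

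**4. Power with and without exclusion**

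Assume that a share w of patients in each arm has the finding and that these patients have the 23% rate. The TKA arm then stays at 23% either way.

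- Excluded: 40×0.9×(1−w) per arm, 60% against 23%.
- Retained as allocated: 36 per arm, with a Bi-UCKA rate of 0.60(1−w) + 0.23w.

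| w | Excluded: n per arm, power | Retained: Bi-UCKA rate, power |
|---|---|---|
| 5% | 34.2, 0.892 | 58.2%, 0.876 |
| 10% | 32.4, 0.874 | 56.3%, 0.838 |
| 15% | 30.6, 0.854 | 54.5%, 0.795 |

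Under this assumption, retention gives lower power than exclusion. The argument for retention is therefore the validity of the comparison, not power.

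**The case against.** The best defence is that the rule is mandatory, pre-specified and written for both arms, and that it rests on a feature present before randomisation. Section 8 already excludes patello-femoral disease above grade III. If the lateral facet means that of the patella, which the text does not say, the rule applies an eligibility criterion at the moment it becomes visible. Section 11.1 describes the trial as explanatory and concerned with efficacy, and a symmetric exclusion is defensible there. This stands as far as it goes: equal detection produces no bias. It does not show that detection will be equal, and it does not make the analysis intention to treat.

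Three stronger readings are tempting, and the documents do not support them.

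- A reader might infer that harder knees are removed mainly from the Bi-UCKA arm. No passage shows this. The incentive differs between arms, but unequal detection is plausible rather than demonstrated.
- A reader might take the gap between 60% and the diluted rates above (1.9, 3.7 and 5.6 points at 5%, 10% and 15%) as the bias from differential exclusion. It is not. With withdrawn patients at 23%, fully symmetric withdrawal gives the same gap. It measures dilution: the effect in eligible knees against the effect in all randomised knees.
- A reader might infer that the general discontinuation list drops patients from the analysis, including any Bi-UCKA converted to TKA. The list permits discontinuation but does not say that data are discarded, and it does not mention conversions. The separate per-protocol analysis in Section 16 suggests that patients not treated as intended stay in the intention-to-treat set. That part of Section 13 is a gap in wording and secondary here.

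**Conclusion.** The conflict holds on the text. Section 13 withdraws randomised patients on a finding judged by a surgeon who knows the allocation and provides no follow-up for them, while Section 16 declares an intention-to-treat primary analysis.

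The bias is possible but not established, and its size cannot be derived from the documents. Under the assumptions shown (40% and 10% biphasic rates, no detection in the TKA arm) it is 1.5 to 3.0 points at 5% to 10% prevalence, with a type I error of 0.052 to 0.058. That is small beside the planned 37-point difference. It grows with prevalence and is zero if detection is equal. The reason to act is the contradiction with the declared primary analysis and the open route for allocation-aware exclusion, not a large numerical effect.

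**What to change.** Leave the surgery given unchanged and reconcile Sections 13 and 16:

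- State that every randomised patient who does not withdraw consent stays in scheduled follow-up and in the primary intention-to-treat analysis in the allocated arm, whatever is found or implanted.
- Move the exclusion of grade 4 cases found in theatre to a per-protocol or sensitivity analysis.
- In the general discontinuation list, say that follow-up and data are retained when the reason is ineligibility or protocol deviation.
- Report withdrawals by arm and reason.

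Timing limits what can be recovered. Protocol version 4.2 is dated March 2021, Table 3 shows recruitment ending in March 2018, and Section 21 puts the end of 1-year data collection at July 2019. Where 1-year visits have passed, report the withdrawals by arm, treat the missing outcomes in a sensitivity analysis, and resume later follow-up with consent.

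The cost is wording, some visits for the patients concerned, and a diluted effect estimate. If those patients have a 23% biphasic rate, power with 36 per arm is about 0.88 when 5% of patients have the finding and 0.84 when 10% do, so retention does not by itself preserve 90%.
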